8.4. Completion of a Patient's Participation in the Study

Patients will be considered to have completed participation in this study once the Week 284 assessments have been completed. Patients may continue in the study for a period up to and including 284 weeks, based on the judgement of the Investigator (described further in Section 7.1); however, a Safety Follow-up visit will occur approximately 4 weeks after the last eteplirsen dose administered, regardless of the patient's duration in the study.

The length of a patient's participation will be calculated from the time the informed consent form is signed until completion of the Safety Follow-up visit (approximately 4 weeks after the last dose of eteplirsen is administered).

8.5. Completion of the Study

This study will be considered to have been completed upon the last visit of the last patient who had their treatment extended (and the 4-week Safety Follow-up) to Week 288, or transitioned to the commercially available product if available.

8.6. Patient Withdrawal Criteria

Any patient can decide to withdraw from study participation at any time for any reason. In addition, the Sponsor may decide to stop the study participation of any patient as deemed necessary. The Investigator may also stop the study participation of any patient at any time.

Reasons for withdrawal from this study include, but are not limited to:

- The patient was erroneously included in the study (ie, was found to not have met the eligibility criteria).
- The patient experiences an intolerable or unacceptable AE.
- The patient is unable to comply with the requirements of the protocol.
- The patient participates in another investigational study without the prior written authorization of the Sponsor.

The Investigator or study staff will document the reason(s) for treatment discontinuation.

Patients who have received at least 1 dose of study treatment and who are withdrawn from treatment within 28 days after a functional assessment visit will be asked to return for an Early Termination (Week 284) visit approximately 28 days after their last dose of eteplirsen. Patients who receive at least 1 dose of study treatment and are withdrawn from treatment more than 28 days after a functional assessment visit will be asked to complete all Early Termination (Week 284) assessments within approximately 28 days after the last dose of eteplirsen.

Patients withdrawn from treatment will not be replaced.

8.7. Study Discontinuation

If the Sponsor, the Investigator, the Medical Monitor, the study monitor, Institutional Review Board (IRB)/Independent Ethics Committee (IEC), or appropriate regulatory officials discover conditions arising during the study that indicate this study should be halted, or that a study site should be terminated, appropriate action may be taken after consultation among (at a minimum) the Sponsor, the Investigator, the IRB/IEC, and the Medical Monitor.

Conditions that may warrant termination of the study or an individual study site include, but are not limited to, the following:

- The discovery of an unexpected, serious, or unacceptable risk to patients enrolled in the study
- A decision by the Sponsor to suspend or discontinue testing, evaluation, or development of the product
- Failure of the Investigator to comply with pertinent regulations of the IRB/IEC or appropriate regulatory authorities
- Failure of the Investigator to comply with the protocol
- Submission of knowingly false information from the research facility to the Sponsor, the study monitor, the IRB/IEC, or appropriate regulatory authority
- Insufficient adherence to protocol requirements consistent with the European Clinical Trial Directive 2001/20/EC

9. TREATMENT OF PATIENTS

9.1. Investigational Product

Eteplirsen drug product is supplied as a sterile, phosphate-buffered saline solution in single-use, 2-mL vials, each containing 2 mL of eteplirsen at 50 mg/mL. The solution is a clear to slightly opalescent and colorless liquid that may contain white to off white particles. Eteplirsen will be administered once a week by IV infusion.

9.1.1. Packaging and Labeling

Please refer to the study-specific Pharmacy Manual for information on packaging, labeling, and preparation instructions.

The label text for the IP will, at a minimum, include the following information: product name/identifier, cautionary statement, lot number (or alternative code), storage conditions, and the name of the Sponsor, pursuant to regional requirements.

9.1.2. Storage

Vials of IP must be stored in a secured, limited-access area with appropriate temperature recording, controls, and monitoring. Details for storage can be found in the study-specific Pharmacy Manual.

9.2. Treatments Administered

Eligible patients will receive a once weekly IV infusion of eteplirsen for up to 284 weeks. Eteplirsen should be prepared for dosing by following the steps detailed in the study-specific Pharmacy Manual.

Patients will receive the **ccc** mg/kg dose of eteplirsen while in this study. The period from Baseline through Week 284 will be considered the “Treatment Period.”

The following guidelines for the timing of dosing should be followed throughout the study:

- Patients should receive eteplirsen once every 7 days starting on Week 1. A window of ± 3 days from the scheduled dose is acceptable after the first infusion.
- Patients may not receive two (2) separate doses of eteplirsen within the same 60-hour period.
- The Medical Monitor should be contacted in the event of ≥ 2 consecutive missed doses.

Week 284 will be followed by a Safety Follow-up Period of up to 4 weeks. Patients may transition to commercially available product if commercially available eteplirsen is available. Home infusion of the study drug may be available.

The administered dose is calculated by patient weight, which will be collected on a weekly basis and used to calculate the dose to be administered at the next visit(s). For example, the weight collected at Week 2 will be used to calculate the doses to be infused during the Week 3 visit. Refer to the Pharmacy Manual for more details on dosing administration.

9.2.1. Dose Modification, Reduction, or Delay

9.2.1.1. Dose Interruption

If a patient experiences an AE that requires interruption of eteplirsen administration for ≥ 2 consecutive doses, the Investigator will consult with the Medical Monitor to determine whether the patient may resume study treatment.

Stopping rules are provided in Section [9.6](#).

9.3. Randomization and Blinding

This is an open-label study, and therefore all patients will receive eteplirsen without blinding.

9.4. Prior and Concomitant Medications

No other medications may be administered concomitantly during the eteplirsen infusion.

The following therapies are not permitted during the conduct of this study:

- Previous or current investigational agents (with the exception of drisapersen: patients may be included in the study if they have not received drisapersen for 6 months prior to the Week 1 study dose)
- Immunosuppressants (other than oral or systemic corticosteroids; the corticosteroid should not be administered during the infusion of eteplirsen)
- Previous (within 12 weeks prior to the Week 1 dose) or current systemic aminoglycoside antibiotic or statin

In general, drug therapies that are not excluded per the entry criteria, including over-the-counter medications, may be used before enrollment and throughout the study. However, the number of over-the-counter medications should be limited and the dosage of any such medication should be constant for at least 1 month prior to starting study treatment and throughout the study, unless clinically indicated.

The Investigator should contact the Medical Monitor if unsure about changing a specific medication.

9.5. Treatment Compliance

Treatment compliance will be assessed via compliance with scheduled weekly infusions.

9.6. Rules for Dose Interruption

The following situations could result in dose interruption of a single patient:

- Any SAE considered to be related to eteplirsen
- See Section [10.3.4](#) for Safety Monitoring, Additional Investigations and Stopping Rules

If a patient meets one of the above criteria, the study monitor should be immediately notified, and dosing should be suspended until the patient's safety information can be reviewed by the DMC. Dosing may resume only after approval of the DMC, Sponsor, and Investigator, and after approval of a substantial amendment by the competent authority.

Conditions that may warrant interrupting dosing for all patients in the study for additional safety review include, but are not limited to:

- Any SAE of life-threatening or fatal outcome assessed as related by the Investigator
- > 2 patients with severe AEs that result in interruption of individual patient dosing (described earlier in Section 9.6)
- Any unexplained or drug-related organ failure (eg, liver or renal failure)

The DMC will monitor safety data on an ongoing basis. If the DMC determines that the criteria for study interruption are met, dosing will be suspended until all available patient information related to the event(s) of interest can be reviewed in more detail. Discontinuation of dosing for an individual patient may occur based on the recommendation of the DMC, investigator, the patient, and the local Independent Ethics Committee (IRB/IEC).

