10.3.4. Safety Monitoring, Additional Investigations and Stopping Rules

10.3.4.1. Safety Monitoring for Liver Chemistry Tests

Liver chemistry tests need to be monitored as specified in the Schedule of Events ([Table 2](#)).

Initial abnormal liver chemistry test result(s) needs to be confirmed if:

- Gamma-glutamyl transferase (GGT) or Glutamate dehydrogenase (GLDH) or Aspartate aminotransferase (AST) or Alanine aminotransferase (ALT) measurement is $> 3 \times$ the upper limit of normal (ULN) (or $> 2 \times$ Baseline value if the Baseline value was $>$ ULN) at any time during the study.

Patients with confirmed liver chemistry test results (as above) need to have their liver chemistry tests (GGT, GLDH, ALT, AST, alkaline phosphatase), international normalized ratio [INR] and total bilirubin) retested 2 or 3 times weekly. Frequency of retesting can decrease to once a week or less if abnormalities stabilize or the trial drug has been discontinued and the subject is asymptomatic.

Additional Investigations:

Patients with confirmed abnormal liver chemistry test results (as above) are recommended to have the following evaluations performed:

- Obtaining a more detailed history of symptoms and prior or concurrent diseases.
- Obtaining a history of concomitant drug use (including nonprescription medications and herbal and dietary supplement preparations), alcohol use, recreational drug use, and special diets.
- Ruling out acute viral hepatitis types A, B, C, D, and E; autoimmune or alcoholic hepatitis; Non-Alcoholic SteatoHepatitis; hypoxic/ischemic hepatopathy; and biliary tract disease.
- Obtaining a history of exposure to environmental chemical agents.
- Additional liver evaluations, including gastroenterology/hepatology consultations, hepatic computed tomography (CT) or magnetic resonance imaging (MRI) scans, may be performed at the discretion of the Investigator, in consultation with the Sponsor Medical Monitor.

Stopping Rules for Liver Test Results:

In the event of laboratory results meeting the following criteria, **and the event is without an alternative explanation as discussed with the Sponsor Medical Monitor**, dosing of a patient with eteplirsen will be stopped permanently; values that are not confirmed due to failure to retest or missing lab values will be presumed confirmed:

- GGT or GLDH $> 8 \times$ ULN, which is confirmed
- GGT or GLDH $> 5 \times$ ULN, which is confirmed and persists for ≥ 2 weeks

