10.3.4.3. Safety Monitoring for Hypersensitivity

Patients will be monitored for occurrence of allergic reactions primarily via monitoring adverse events as specified in the Schedule of Events ([Table 2](#)). Patients will be instructed to promptly report any signs or symptoms of fever or constitutional symptoms that may arise during the study and the Investigator needs to closely evaluate all potential causes, including concomitant illness.

Additional Investigations:

Patients who experience significant or persistent constitutional symptoms need to be discussed with the Sponsor Medical Monitor to determine whether additional monitoring or laboratory tests are required. Additional evaluations including immunology consultation, tests for allergic reactions (absolute eosinophils, serum/plasma tryptase), may be performed at the discretion of the Investigator in consultation with the Sponsor Medical Monitor.

Stopping Rules for Hypersensitivity AEs:

In the event of a confirmed hypersensitivity AE meeting the following criteria, **and the event is without an alternative explanation as discussed with the Sponsor Medical Monitor**, dosing of a patient with eteplirsen will have their treatment permanently discontinued.

- Anaphylaxis, anaphylactoid reaction, or angioedema
- Any serious allergic reaction

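### The dose rationale contradicts itself, Section 5.5 assigns oversight to a committee no operative section uses, and three rules on holding and resuming dosing are not reconciled

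*Combined protocol and SAP*

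**What the plan says.** **Dose.** Section 7.2 (Dose Selection Rationale) reports that two doses were compared in Study 4658-us-201 and its extension, that their dystrophin effects were similar, and that the lower was therefore selected as the cautious option. The study dose is redacted, but 30 and 50 mg/kg stand unredacted as the two weekly doses compared. The closing paragraph of the same section says the safety data so far, obtained at between a third and a half of this study's dose, raise no significant concern. Section 5.5 (Benefit and Risk Assessment) twice describes the dose here as higher: once when warning of more frequent or severe reactions, and once when arguing for benefit.

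**Oversight.** Section 5.5 assigns the open-label period to a Safety Review Committee and a double-blind period to a DMC. Section 9.3 states that the study is open-label. Sections 9.6 and 10.3.5.1 name only the DMC.

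**Dosing holds.** Section 9.6 lists two single-patient grounds for a hold: a related SAE, and a pointer to Section 10.3.4 "for Safety Monitoring, Additional Investigations and Stopping Rules". When either is met, "the study monitor should be immediately notified, and dosing should be suspended" until the DMC has reviewed the patient. Then: "Dosing may resume only after approval of the DMC, Sponsor, and Investigator, and after approval of a substantial amendment by the competent authority". Section 9.6 adds: "Discontinuation of dosing for an individual patient may occur based on the recommendation of the DMC", among other parties. Section 10.3.4 attaches a permanent stop to its liver, renal and platelet criteria ("dosing of a patient with eteplirsen will be stopped permanently") and its hypersensitivity criteria ("dosing of a patient with eteplirsen will have their treatment permanently discontinued"), provided "the event is without an alternative explanation as discussed with the Sponsor Medical Monitor". Section 9.2.1.1 covers an adverse event that keeps a patient off two or more doses in a row: the Investigator consults the Medical Monitor, and that consultation determines whether dosing restarts. It ends "Stopping rules are provided in Section" 9.6.

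**The concern.** Safety and tolerability is the primary objective, in young children dosed weekly for up to 284 weeks. The benefit-risk case depends on whether earlier safety experience was gathered at, above or well below the dose given here, and the protocol says more than one of these things. The safeguard that Section 5.5 offers against a higher dose is review by a body that has no role elsewhere in the protocol. When a patient's dosing is held, the approximately 4 sites need one rule for restarting it. They have three texts with different triggers and decision-makers.

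**Working it through.** **1. Dose relation**

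Inputs: the selected dose is the lower, L, of two tested doses L < H (Section 7.2, main text); the ratio of earlier dose to study dose is 1/3 to 1/2, or 0.33 to 0.50 (Section 7.2, closing paragraph); visible tested doses are 30 and 50 mg/kg (Section 7.2).

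Let r = earlier dose / study dose.

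- If the study dose is L, then r = L/L = 1.0 and r = H/L > 1. Neither lies in 0.33 to 0.50 for any L and H, so the stated ratio is not reproduced and the redacted value is not needed to see this.
- With the visible figures and a study dose of 30: r = 30/30 = 1.00 and 50/30 = 1.67.
- With a study dose of 50: r = 30/50 = 0.60 and 50/50 = 1.00. Still outside the band.
- In reverse, for 30 mg/kg to be 1/2 to 1/3 of the study dose, that dose would be 60 to 90 mg/kg; for 50 mg/kg, 100 to 150 mg/kg. All exceed 50 mg/kg, the highest unredacted dose in the text.

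Side check on patient counts in Sections 5.3 and 7.2: 149 + 6 = 155, matching the stated 155. The counts agree; the dose statements do not. Section 5.5 and the closing paragraph of 7.2 point the same way, and both conflict with the main text of 7.2. The contradiction therefore lies inside Section 7.2 as well as between sections.

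**2. Oversight**

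No arithmetic applies. Section 5.5 presupposes an open-label and a double-blind period. Section 9.3 rules out the second. Taken literally, Section 5.5 leaves the DMC no period in which to act, yet Section 9.6 has it monitor throughout and approve each resumption, and Section 10.3.5.1 lists what it reviews. The abbreviations list has the DMC only, and the table of contents has no section on either body.

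**3. Dosing holds**

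Permanent-stop criteria in Section 10.3.4: 4 liver + 5 renal + 2 hypersensitivity + 1 platelet = 12.

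| | 9.2.1.1 | 9.6 | 10.3.4 |
|---|---|---|---|
| Trigger | AE, two or more doses in a row interrupted | Related SAE, or Section 10.3.4 | Any of 12 criteria, no alternative explanation |
| Result | Resumption considered | Hold until DMC review; can be lifted | Permanent stop |
| Who | Investigator with Medical Monitor | DMC, Sponsor, Investigator, competent authority | Discussion with Sponsor Medical Monitor; no one named as deciding |

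Three cases show where the texts meet:

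- *Platelets below 50,000/mm³, unexplained.* Section 9.6 holds dosing and describes a way back; Section 10.3.4.4 ends dosing. Hold, review, then permanent stop satisfies both, but only if the way back is closed at that point. The protocol does not say that it is.
- *Related SAE, two weekly doses missed.* Sections 9.2.1.1 and 9.6 both apply. One has two people determine resumption; the other requires four approvals, one of them for a substantial amendment. Neither says it yields to the other.
- *Retest threshold only, for example urinary red cells above 1/hpf.* Section 10.3.4.2 asks for repeat testing. Section 9.6 cites the whole of Section 10.3.4, so on a literal reading this result also triggers a hold that needs an amendment to lift. The rhabdomyolysis text under 10.3.4.4 has no stopping rule at all, yet falls under the same reference.

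**The case against.** The strongest reply concerns dosing holds. A reader might infer that Sections 9.6 and 10.3.4 flatly contradict each other, one reversible and one permanent for the same event. The documents do not support that. Section 9.6 sets a minimum condition for resuming and grants no right to resume. The permanent stop applies only when no alternative explanation is found, so the two outcomes can attach to different facts. The clause saying that discontinuation may occur adds grounds and does not soften the permanent stop. Nor is it right that the sections are unlinked: 9.2.1.1 points to 9.6, and 9.6 points to 10.3.4 by its full title. Section 9.2.1.1 could likewise be a first step to which 9.6 adds approvals. All of this stands. What remains is that the sequence, the governing section, the scope of the reference and the person who rules on an alternative explanation are not written.

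Two further inferences should be resisted. The list in Section 10.3.5.1 is narrower than the stopping criteria, but it states what DMC review will include, not its limit, and 9.6 already sends held patients to the DMC. And the planned maximum of 15 patients is enrolment, not the number affected by the hold rules.

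On dose, one may say that the figures are redacted and that calling the selected lower dose the study dose is an inference. It is one, but Section 7.2 presents that selection as the rationale for the dose used here. The redaction does, however, prevent any conclusion that patients are dosed above tested levels.

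On oversight, Section 5.5 is introductory and gives sites no instruction involving the Safety Review Committee. That limits the consequence; it does not make the text correct.

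**Conclusion.** The point holds in three parts of unequal strength.

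- **Dose basis: wrong as written.** The earlier-to-study ratio is at least 1.0 in one part of Section 7.2 and 0.33 to 0.50 in another, with Section 5.5 siding with the latter. This assumes only that the lower dose selected in 7.2 is the dose of this study. The size of the discrepancy in mg/kg cannot be determined.
- **Oversight: wrong as written.** Section 5.5 describes a study period that does not exist and a committee that no other section uses.
- **Dosing holds: conflict and ambiguity, not outright contradiction.** Section 9.6 taken literally covers retest thresholds as well as the 12 stopping criteria. The resumption routes in 9.2.1.1 and 9.6 differ, and nothing says whether resumption is closed after a permanent-stop criterion is met. This reaches only patients who meet such a criterion.

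No effect on an endpoint or an analysis is claimed. These are inconsistencies in the safety rules and the stated risk basis of a safety study. They should be fixed, and the repair is cheap.

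**What to change.** One protocol amendment should:

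- make Section 5.5 and both parts of Section 7.2 agree on how the study dose relates to the doses behind the safety data;
- name one oversight body consistently in Sections 5.5, 9.6 and 10.3.5.1, and remove the double-blind text;
- reconcile Sections 9.2.1.1, 9.6 and 10.3.4, stating which part of 10.3.4 the reference in 9.6 means, which resumption route governs, who rules on an alternative explanation, and whether resumption is closed once a permanent-stop criterion is met.

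Which dose and which clinical rule apply is for the sponsor to state. The cost is the IRB/IEC and regulatory authority review that Section 14.2 requires, plus notice to the sites. No patients, visits or procedures are added.

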10. STUDY ASSESSMENTS

10.1. Study Schedule of Events

A detailed schedule of the study assessments and time points is shown in [Table 2](#).

10.2. Baseline Assessments

10.2.1. Informed Consent

Written informed consent from the patient and/or their parent(s)/legal guardian(s) to participate in this study must be obtained prior to beginning any of the procedures for this study.

10.2.2. Other Assessments

Baseline assessments will also include clinical safety laboratory assessments, vital signs, physical examination, height/ulnar length, weight, 12-lead ECG, assessment of prior and concomitant medications/therapies, and assessment of AEs.

10.3. Safety Assessments

10.3.1. Physical Examination

The Investigator or a medically qualified subinvestigator will perform physical examinations at designated study visits, including examination of general appearance; head, ears, eyes, nose, and throat; heart; lungs; chest; abdomen; skin; lymph nodes; musculoskeletal system and neurological system.

